#### 7.4.1.1.1 Dose Reduction Levels

Dose reduction levels of carfilzomib for toxicity management of individual subjects are provided in Table 7-2. Subjects that require dose reduction may have the dose escalated according to specific rules, see Section 7.4.1.1.4. Subjects should have the starting nominal dose of carfilzomib (56 mg/m² or 70 mg/m² based on treatment arm) on day 1 cycle 3 reduced by the same number of dose levels and the same percentage dose reduction as they were reduced during cycle 2, see Table 7-2 for dose level reductions. Subjects who require fifth dose reductions should discontinue carfilzomib.

Table 7-2. Dose Decrements for Carfilzomib

Nominal	First Dose Reduction	Second Dose Reduction	Third Dose Reduction	Fourth Dose Reduction
Dose a, b	Dose -1	Dose -2	Dose -3	Dose -4
(mg/m  )	(mg/m²)	(mg/m²)	(mg/m²)	(mg/m²)
20	15	11	Discontinue	
27	20	15	11	Discontinue
56	45	36	27	20
70	56	45	36	27

<sup>a If dose reduction of carfilzomib is required on Cycle 1 Day 1 or Cycle 1 Day 2 for any reason other than mild hepatic insufficiency, the investigator should contact the medical monitor to discuss the situation, before any additional doses of carfilzomib are administered.

<sup>b For patients with baseline chronic hepatic impairment (mild), reduce the starting and subsequent doses of carfilzomib by 25% (ie, 15 mg/m² day 1 and 2 of cycle 1 and 42 mg/m² day 8 cycle 1 and thereafter).

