**Date:** 20 May 2019 **Page 21 of 132** 

Table 2-1. Schedule of Activities

	Screening a b				Tre	eatr	nen	t P	erio	d				Safety	
	(up to			Су	cle	1-2				C	ycl	e 3-	12	FU c (30	
PROCEDURE	21 days before Day 1)	Day 1	2	8	9	15	16	22	23	1	8	15	21	[+3] days post last dose)	Notes
Bone Lesion Assessment b	х														Screening and will be repeated if worsening clinical symptoms suggest PD, or as clinically indicated. (see Section 12.8 for IMWG criteria)
Plasmacytoma evaluation b	х														See Section 9.2.2.3. Only required at screening in subjects if clinically suspected and to confirm response (if performed at screening, see Section 12.8 for IMWG criteria)
Bone marrow aspirate with FISH b	Х														Bone marrow aspirate is required at screening and to confirm a response of CR (see Section 12.8 for IMWG criteria). FISH is only required at screening.
CLINICAL OUTCOME ASSESSM	MENTS														
EORTC QLQ-C30		Х								Х				X	During treatment period, these
EORTC QLQ-MY20		Х								Х				Х	questionnaires must be completed on day 1 of each cycle prior to dosing.
Amgen Satisfaction and Convenience Questionnaire		x								x				Х	During treatment period, these questionnaires must be completed on day 1 of each cycle prior to dosing, starting with C2D1. Items 8-11 to be collected only once at end of treatment or at completion of the trial.

Page 4 of 7

**Protocol Number:** 20170596

**Date:** 20 May 2019 Page 22 of 132

Table 2-1. Schedule of Activities

	Screening a b				Tre	eatr	nen	t Pe	erio	d				Safety	
	(up to			Су	cle	1-2				С	ycl	e 3-′	12	FU c (30	
PROCEDURE	21 days before Day 1)	Day 1	2	8	9	15	16	22	23	1	8	15	21	[+3] days post last dose)	
STUDY TREATMENT															
Kd ARM															
Carfilzomib administration h		X	×	X	X	X	×			x	x	x			Cycle 1: 20 mg/m² on days 1 and 2; 56 mg/m² on days 8, 9, 15, and 16 Cycle 2: 56 mg/m² Cycles 3-12: 70 mg/m² For subjects with baseline hepatic function abnormalities (bilirubin or AST > ULN), see Section 7.1.1.2.1 for modification of the initial dose. For cycle 3, for subjects who were previously dose reduced, see Section 7.1.1.2 for starting dose.
Dexamethasone administration h		x	х	X	X	X	X	Xi	Xi	х	х	х			Cycles 1-2: 20 mg Cycles 3-12: 40 mg For subjects ≥ 75 years of age, see Section 7.4.1.2 for dose modification.

**Protocol Number:** 20170596

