# 5.4.2 Justification for Investigational Product Dose for KRd and KPd Arms

The safety experience from 56 subjects with RRMM with weekly KRd 56 mg/m $^2$  (n = 10) or 70 mg/m^2 (n = 46) in Study CFZ013 (NCT02335983) has not identified any safety concerns which would preclude the investigation of KRd 56 mg/m^2 weekly in this study. The subject incidence of grade ≥ 3 treatment-emergent adverse events was 70.0% in the KRd 56 mg/m² group and 69.6% in the KRd 70 mg/m² group. Grade ≥ 3 adverse events reported in more than 2 patients were thrombocytopenia (56 mg/m $^2$ , n = 2; 70 mg/m^2, n = 4), neutropenia (56 mg/m^2, n = 1; 70 mg/m^2, n = 4), anemia (56 mg/m^2, n = 2; 70 mg/m^2, n = 3), pneumonia (70 mg/m^2, n = 4), decreased platelet count (56 mg/m^2, n = 1; 70 mg/m^2, n = 3), decreased neutrophil count (56 mg/m^2, n = 2; 70 mg/m^2, n = 2), hypertension (56 mg/m^2, n = 1; 70 mg/m^2, n = 3), and hypophosphatemia (70 mg/m^2, n = 4). There were 3 deaths in the KRd 70 mg/m^2 group (1 each due to cardiac arrest, cardiac disorder, and disease progression). No deaths occurred in the KRd 56 mg/m^2 group (Biran et al. 2018). The median weekly dose of carfilzomib was 53.2 mg/m^2 for subjects administered 20/56 mg/m^2 and 62.4 mg/m^2 for subjects administered 20/70 mg/m^2. The median relative dose intensity of carfilzomib was 90.7 for subjects administered 20/56 mg/m^2 and 88.2 for subjects administered 20/70 mg/m^2. The median weekly dose and the relative dose intensity suggest that 20/56 mg/m^2 weekly dose was tolerable.

Available efficacy results indicated similar efficacy (as determined by ORR) with either KRd 56 mg/m^2 or KRd 70 mg/m^2 (90.0% versus 89.1%, respectively) to the effect previously reported for twice-weekly KRd (27 mg/m^2) in the randomized phase 3 ASPIRE study (Biran et al, 2018).

Based on evidence from phase 2 studies of KPd, weekly doses up to 70 mg/m² in subjects with first relapse and up to 54 mg/m² in subjects with advanced myeloma using a twice-weekly schedule of carfilzomib have been tolerated (Sonneveld et al, 2018;

Protocol Number: 20170596

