## **Organ Function Assessments**

- Hepatic dysfunction within 21 days prior to enrollment (see Section 7.1.1.2.1):
  - bilirubin ≥ 1.5 times the upper limit of normal (ULN)
  - aspartate aminotransferase (AST) or alanine aminotransferase (ALT)
     ≥ 3 times the ULN
- 230 Left ventricular ejection fraction < 40% assessed by transthoracic echocardiogram.
- 231 Severe valvular disease assessed by transthoracic echocardiogram.
- 232 Severe right-ventricular dysfunction assessed by transthoracic echocardiogram.
- 233 Right-ventricular systolic pressure > 40 mm Hg assessed by transthoracic echocardiogram.
- Absolute neutrophil count (ANC) < 1 x  $10^9$ /L within 21 days prior to enrollment. Screening ANC should be independent of growth factor support for  $\geq$  1 week.

Protocol Number: 20170596

**Date:** 20 May 2019 Page 47 of 132

Hemoglobin < 80 g/L within 21 days prior to enrollment. Use of erythropoietic stimulating factors and red blood cell (RBC) transfusions per institutional guidelines is allowed, however most recent RBC transfusion may not have been done within 7 days prior to obtaining screening hemoglobin.

Platelet count <  $50 \times 10^9$ /L ( $\leq 30 \times 10^9$ /L if myeloma involvement in the bone marrow is > 50%) within 21 days prior to enrollment. Subjects should not have received platelet transfusions for at least 1 week prior to obtaining the screening platelet count.

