# 7.1.1.2 Dosage, Administration, and Schedule

For all treatment arms, carfilzomib will be administered at 20 mg/m² on days 1 and 2 of the first cycle (see Table 7-1). For subjects in the Kd arm, carfilzomib will be administered at 56 mg/m² on days 8, 9, 15, and 16 of the first cycle, and then on days 1, 2, 8, 9, 15, and 16 in cycle 2. Starting with cycle 3 through cycle 12, carfilzomib will be administered at 70 mg/m² on days 1, 8, and 15 of each 28-day cycle. For subjects in the KRd and KPd arms, carfilzomib will be administered at 27 mg/m² on days 8, 9, 15, and 16 of the first cycle, and then on days 1, 2, 8, 9, 15, and 16 in cycle 2. Starting with cycle 3 through cycle 12, carfilzomib will be administered at 56 mg/m² on days 1, 8, and 15 of each 28-day cycle.

Protocol Number: 20170596

**Date:** 20 May 2019 Page 50 of 132

At the time of implementation of protocol amendment 3, subjects previously enrolled may have completed more than 2 but less than 6 cycles of twice weekly carfilzomib dosing on the Kd arm as per protocol amendment 2. These subjects should complete the dosing regimen as per protocol amendment 2, (ie, 6 cycles of twice weekly dosing for carfilzomib [Kd 56 mg/m²] transitioning to once weekly dosing for carfilzomib [Kd 70 mg/m²], starting with cycle 7). For these subjects, the schedule of activities outlined per Table 2-1 for cycles 1 and 2 will continue for cycles 1 through 6. At the start of cycle 7, these subjects will then follow the schedule of activities as outlined per Table 2-1 cycles 3 through 12. In addition, the starting nominal dose of carfilzomib on day 1 cycle 7 (which is the initiation of the once weekly carfilzomib dosing for these subjects) should be reduced by the same number of dose levels and same percentage dose reduction as it was reduced to during cycle 6 (which is the twice weekly carfilzomib dosing). Dexamethasone will be administered at a dose of 20 mg once daily on days 1, 2, 8, 9, 15, 16, 22, and 23 cycles 1 through 6 and at a dose of 40 mg once daily on days 1, 8, 15 for the Kd arm for cycles 7 through 12 for these subjects.

All doses should be administered on the scheduled day  $\pm$  2 days, and the day 8 and 15 doses should have at least a 5-day treatment-free interval. The starting dose should be modified for chronic mild hepatic insufficiency per Section 7.1.1.2.1.

Table 7-1. Carfilzomib Dosage

Cycle 1	Cycle 2	Cycles 3-12		
Kd Arm				

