## 7.1.1.2.1 Starting Dose in Hepatic Insufficiency

For subjects with mild hepatic insufficiency during screening, the initial dose of carfilzomib on days 1 and 2 of cycle 1 should be reduced by 25% to 15 mg/m². For subjects in the Kd arm, starting on day 8 and for all subsequent doses of carfilzomib during cycles 1 and 2, the dose should be 42 mg/m² (Brown et al, 2017); the dose in cycle 3 through 12 should be 53 mg/m². For subjects in the KRd and KPd arms, starting on day 8 and for all subsequent doses of carfilzomib during cycles 1 and 2, the dose should be 20 mg/m² as per the protocol and doses in cycles 3 through 12 should be 42 mg/m².

If hepatic function returns to normal, the dose in following cycles may be re-escalated to the full dose per the protocol. For dose modification due to subsequent changes in hepatic function, refer to Section 7.4.1.1.3 (Table 7-4).

Protocol Number: 20170596

**Date:** 20 May 2019 Page 52 of 132

Mild and moderate hepatic dysfunction is defined as:

Mild: bilirubin > 1.0-1.5 x ULN, or AST > ULN with bilirubin ≤ ULN

Moderate: bilirubin > 1.5-3.0 x ULN with any AST

Grade 3 elevation in ALT and/or AST (> 5x ULN)

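### Table 7-2 footnote b prints 42 mg/m² as the 25% hepatic reduction without naming an arm; for KRd and KPd in cycles 1-2 that exceeds the full dose

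*Protocol*

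**What the plan says.** Table 7-2 in Protocol Section 7.4.1.1.1 lists dose decrements for four nominal carfilzomib doses: 20, 27, 56 and 70 mg/m². Footnote b hangs on the nominal-dose column. For a subject with mild chronic hepatic impairment at baseline it cuts both the first and the later doses "by 25% (ie, 15 mg/m² day 1 and 2 of cycle 1 and 42 mg/m² day 8 cycle 1 and thereafter". The footnote is not limited to an arm or to a nominal dose, and its last figure has no end point.

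Section 7.1.1.2.1 gives the doses for the same subjects by arm. All arms receive 15 mg/m² on cycle 1 days 1 and 2. Kd then receives 42 mg/m² through cycle 2, after which "the dose in cycle 3 through 12 should be 53 mg/m²". For KRd and KPd, from cycle 1 day 8 through cycle 2, "the dose should be 20 mg/m² as per the protocol and doses in cycles 3 through 12 should be 42 mg/m²".

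The full doses are in Section 7.1.1.2 and Table 7-1. For the triplets, "For subjects in the KRd and KPd arms, carfilzomib will be administered at 27 mg/m² on days 8, 9, 15, and 16" of cycle 1; cycle 2 is also at 27, and cycles 3-12 are at 56 once weekly. Kd is at 56 twice weekly and then 70 once weekly from cycle 3. Section 7.1.1.2 makes one exception: Kd subjects enrolled earlier who were already past cycle 2 when Amendment 3 took effect stay on 56 twice weekly through cycle 6 and move to 70 at cycle 7.

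**The concern.** The footnote's rule and its worked figure disagree. A 25% cut gives a different dose for each nominal dose, but after day 2 the footnote prints only one. A site reading it for a KRd or KPd subject in cycle 1 or 2 finds a reduced dose of 42 mg/m² where the full dose is 27. That error runs in the unsafe direction: a subject with impaired liver function would receive more carfilzomib per infusion than one with normal liver tests.

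Such subjects can be enrolled in every arm. Hepatic exclusion starts at "bilirubin ≥ 1.5 times the upper limit of normal (ULN" or at AST or ALT of 3 times ULN, while Section 7.1.1.2.1 calls impairment mild as soon as bilirubin, or AST with normal bilirubin, is above ULN.

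For KPd there is a benchmark in Section 5.4.2, which cites as tolerated "weekly doses up to 70 mg/m² in subjects with first relapse", and up to 54 mg/m² in advanced myeloma. Two infusions at the printed figure make 84 mg/m² in a week.

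**Working it through.** **Inputs.** Reduction of 25% (footnote b). Nominal doses of 20, 27, 56 and 70 mg/m² (Table 7-2, Table 7-1). Hepatic doses of 15, 20, 42 and 53 mg/m² (Section 7.1.1.2.1). Printed figure of 42 mg/m² (footnote b).

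**Step 1: reproduce the figures.** Reduced dose = 0.75 × nominal dose.

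- 0.75 × 20 = 15. This matches the footnote and Section 7.1.1.2.1.
- 0.75 × 27 = 20.25, rounded to 20 in Section 7.1.1.2.1.
- 0.75 × 56 = 42. This matches both.
- 0.75 × 70 = 52.5, rounded to 53 in Section 7.1.1.2.1.

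So 42 reproduces only from a nominal dose of 56.

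**Step 2: compare the printed 42 by arm and period (mg/m² per dose).**

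| Arm and period | Full | Section 7.1.1.2.1 | Footnote | Footnote / full | Footnote / 7.1.1.2.1 |
|---|---|---|---|---|---|
| Kd, cycle 1 day 8 through cycle 2 | 56 | 42 | 42 | 0.75 | 1.00 |
| Kd on nominal 70 | 70 | 53 | 42 | 0.60 | 0.79 |
| KRd/KPd, cycle 1 day 8 through cycle 2 | 27 | 20 | 42 | 1.56 | 2.10 |
| KRd/KPd, cycles 3-12 | 56 | 42 | 42 | 0.75 | 1.00 |

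The second row means cycles 3-12 for most Kd subjects. For the previously enrolled subjects held on 56 through cycle 6 it means cycles 7-12; in their cycles 3-6 the nominal dose is still 56, so 42 is right.

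**Step 3: size for KRd and KPd.** Per dose: 42 − 20 = 22 mg/m² too much. Per week of two infusions: 84 against 40 (full dose 54). Affected doses: 4 in cycle 1 plus 6 in cycle 2 = 10. If the printed figure were followed for all ten: 10 × 42 = 420 against 10 × 20 = 200 (full dose 10 × 27 = 270). That is an upper bound; a single dose given in error is +22.

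**Step 4: size for Kd on nominal 70.** Per dose: 53 − 42 = 11 mg/m² too little, a cut of 1 − 42/70 = 40%. Per cycle: 3 × 42 = 126 against 3 × 53 = 159. The upper bound for cycles 3-12, with no re-escalation, is 30 × 42 = 1260 against 30 × 53 = 1590.

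**The case against.** The best reply is that no site needs this parenthetical to find the dose. Table 2-1 tells sites in all three arm rows to "see Section 7.1.1.2.1 for modification of the initial dose"; Section 7.1.1.2 and the hepatic exclusion criterion point to the same place. Table 7-2 is introduced as a tool for managing toxicity. The footnote's operative rule, a 25% cut, is correct in every arm, and the same table has a row for nominal 27 whose first reduction is 20, so a rise from 27 to 42 ought to look wrong. All of this stands and lowers the chance of an actual error.

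It does not remove the contradiction, because the routing also runs the other way. Section 7.1.1.2, when it discusses subjects already reduced by 25% for hepatic abnormalities, refers them to Table 7-2, and Section 10.2.2 cites Section 7.4.1.1.1, where the footnote sits, for chronic mild hepatic impairment.

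On the Kd side the reply is stronger. Section 7.1.1.2 and the paragraph directly above Table 7-2 both carry the cycle 2 percentage reduction over to the cycle 3 starting dose. A Kd subject at 42 (56 less 25%) therefore restarts at 70 less 25%, the 53 of Section 7.1.1.2.1. A site would have to pass over that text and Section 7.1.1.2.1 to give 42 for thirty doses. The Kd part is largely mitigated.

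A reader might infer three stronger things. One is that 42 is wrong for every Kd subject from cycle 3; it is not, because of the previously enrolled subjects still on 56. Another is that triplet subjects will be overdosed; the documents show an inconsistent instruction, not that sites follow it. The third is that adherence or safety results for an arm are distorted; the documents do not say how many subjects have mild impairment at baseline, so nothing supports that.

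**Conclusion.** The footnote is wrong as written. Its worked dose contradicts its own 25% rule and Section 7.1.1.2.1 wherever the nominal dose after cycle 1 day 2 is not 56. The part that matters is KRd and KPd from cycle 1 day 8 through cycle 2: 42 printed against 20 correct, 22 mg/m² per dose above the intended dose and 15 mg/m² (42 − 27) above the full one. The Kd part, 42 against 53 once the nominal dose is 70, is a real inconsistency of lesser weight because other text gives the right dose.

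This rests on reading the footnote as applying to all arms, which its position on a shared table and its silence on arm both support. The cumulative figures further assume that the printed dose is followed throughout, without correction or re-escalation, and are upper bounds. The issue is the dose to an individual subject. It should be corrected; it does not call the design or the analyses into question.

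**What to change.** Replace the parenthetical in footnote b with doses tied to the nominal dose: *(ie, nominal 20 to 15, 27 to 20, 56 to 42, 70 to 53 mg/m²; see Section 7.1.1.2.1)*.

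Do not key the replacement to cycle numbers. A line giving Kd 53 mg/m² in cycles 3-12 would, for the previously enrolled subjects still on 56 twice weekly through cycle 6, set a dose only about 5% below full (53/56 = 0.95) and 11 mg/m² above the correct 42. Section 7.1.1.2.1 is itself written by cycle without an exception for these subjects, which is why the nominal-dose mapping should appear in the footnote and not only a cross-reference.

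The cost is one footnote in the next amendment, or a dosing letter to sites. Every value is already in the protocol, and no new test, CRF field or analysis is needed.

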**Date:** 20 May 2019 **Page 23 of 132** 

Table 2-1. Schedule of Activities

	Screening a b				Tre	eatr	ner	ıt P	erio	d			Safety FU°		
	(up to 21 days			Су	cle	1-2				С	ycle	3-1	2	(30 [+3] days post	
PROCEDURE	before Day 1)	Day 1	2	8	9	15	16	22	23	1	8	15	21	last dose)	
KRd ARM															
Carfilzomib administration h		X	×	×	×	×	×			X	x	x			Cycle 1: 20 mg/m² on days 1 and 2; 27 mg/m² on days 8, 9, 15, and 16 Cycle 2: 27 mg/m² Cycles 3-12: 56 mg/m² For subjects with baseline hepatic function abnormalities (bilirubin or AST > ULN), see Section 7.1.1.2.1 for modification of the initial dose. For cycle 3, for subjects who were previously dose reduced, see Section 7.1.1.2 for starting dose.
Lenalidomide administration				Day	/s 1	to	21 (	of e	ach	сус	le				25 mg
Dexamethasone administration h		Х	х	х	х	х	х	Xi	Xi	Х	х	х			Cycles 1-2: 20 mg Cycles 3-12: 40 mg For subjects ≥ 75 years of age, see Section 7.4.1.2 for dose modification.

Page 6 of 7

**Protocol Number:** 20170596

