D1, 2: 20 mg/m  D8, 9, 15, 16: 56 mg/m 	D 1, 2, 8, 9, 15, 16: 56 mg/m 	D1, 8, 15: 70 mg/m 		
KRd Arm	KRd Arm			
D1, 2: 20 mg/m  D8, 9, 15, 16: 27 mg/m 	D 1, 2, 8, 9, 15, 16: 27 mg/m 	D1, 8, 15: 56 mg/m 		
KPd Arm				
D1, 2: 20 mg/m  D8, 9, 15, 16: 27 mg/m 	D 1, 2, 8, 9, 15, 16: 27 mg/m 	D1, 8, 15: 56 mg/m 		

D = day

Subjects receiving carfilzomib at doses less than the protocol planned dose (56 mg/m^2 or 27 mg/m^2 based on treatment arm) during cycle 2 may have been reduced by 1 or more dose levels and/or by 25% for hepatic function abnormalities. Subjects should have the starting nominal dose of carfilzomib (70 mg/m^2 or 56 mg/m^2 based on treatment arm) on day 1 cycle 3 reduced by the same number of dose levels and the same

Protocol Number: 20170596

**Date**: 20 May 2019 Page 51 of 132

percentage dose reduction as they were reduced during cycle 2, see Table 7-2 for dose level reductions.

Carfilzomib is to be administered as an IV infusion over 30 (± 5) minutes. Subjects should receive 250 mL of normal saline or equivalent IV fluid prior to and after each dose during cycle 1. After cycle 1, at the discretion of treating physician, subjects may receive up to but no more than 250 mL of normal saline or equivalent fluid prior to each dose of carfilzomib. For subjects at risk of TLS, see Section 7.1.4.3.

Mechanical infusion pumps are recommended, but gravity-dependent infusions are permitted if the 30-minute infusion duration can be reliably maintained. Carfilzomib infusion must occur at a facility capable of managing hypersensitivity reactions.

Each subject's first dose will be calculated based upon baseline BSA per the Mosteller formula. In subjects with BSA of greater than  $2.2 \text{ m}^2$ , the dose should be capped based on a BSA of  $2.2 \text{ m}^2$ . The dose for each subject should not be revised unless the subject experiences a change in body weight of  $\geq 20\%$  compared to baseline or last calculation of BSA, in which case the BSA and dose should be recalculated. The dose can also be modified in response to toxicity following the dose modification guideline tables (see Section 7.4).

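### Table 7-2 footnote b gives 42 mg/m² as the hepatic-reduced carfilzomib dose with no arm named; in KRd and KPd through cycle 2 the intended dose is 20 mg/m² and the full dose only 27 mg/m²

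*Protocol*

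**What the plan says.** Two places in the current protocol (Amendment 4) give carfilzomib doses for mild hepatic impairment at baseline.

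- **Section 7.4.1.1.1, Table 7-2, footnote b.** The footnote hangs on the nominal-dose column header, so it covers all four rows (20, 27, 56 and 70 mg/m²). It tells sites to "reduce the starting and subsequent doses of carfilzomib by 25" percent and then states what that means: "15 mg/m² day 1 and 2 of cycle 1 and 42 mg/m² day 8 cycle 1 and thereafter". No arm is mentioned.
- **Section 7.1.1.2.1.** All arms start at 15 mg/m² on cycle 1 days 1 and 2. Kd then receives 42 mg/m² through cycle 2, after which "the dose in cycle 3 through 12 should be 53 mg/m²". For KRd and KPd from day 8 through cycle 2, "the dose should be 20 mg/m² as per the protocol and doses in cycles 3 through 12 should be 42 mg/m²".

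The unreduced KRd and KPd dose from cycle 1 day 8 through cycle 2 is 27 mg/m² (Section 7.1.1.2 and Table 7-1). No other arm uses the 27 row of Table 7-2.

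The text after Table 7-1 says that patients below the planned dose in cycle 2 "may have been reduced by 1 or more dose levels and/or by 25% for hepatic function abnormalities". It sets their cycle 3 dose by taking the same number of levels and the same percentage off the arm's once-weekly nominal dose. Section 7.4.1.1.1 repeats this rule: "the same percentage dose reduction as they were reduced during cycle 2".

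**The concern.** The footnote's figure fits Kd in cycles 1-2, and nothing confines it to that arm and period. Read literally for a triplet patient, it makes a dose reduction into a dose increase, starting on cycle 1 day 8.

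Such patients can enrol. Section 6.2 excludes bilirubin at or above 1.5 times ULN and AST or ALT at or above 3 times ULN. Mild impairment in Section 7.1.1.2.1 starts just above normal, so most of its range is eligible. Footnote a to the same table also exempts mild hepatic insufficiency from the call to the medical monitor that other reductions on cycle 1 days 1-2 require, which removes one possible check.

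At stake is about a doubling of carfilzomib, given with lenalidomide or pomalidomide, in patients whose dose was meant to be lowered.

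**Working it through.** **Inputs.** Nominal doses: 20, 27, 56 and 70 mg/m² (Tables 7-1 and 7-2). Reduction: 25%. Triplet doses per patient: 6 in cycle 1 (2 at the starting dose, 4 from day 8), 6 in cycle 2 and 3 × 10 = 30 in cycles 3-12, 42 in all.

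**Reproducing the footnote's figure.** Reduced dose = 0.75 × nominal dose:

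| Arm and period | Nominal | 0.75 × nominal | Section 7.1.1.2.1 | Footnote b |
|---|---|---|---|---|
| All arms, cycle 1 days 1-2 | 20 | 15 | 15 | 15 |
| Kd, cycle 1 day 8 through cycle 2 | 56 | 42 | 42 | 42 |
| Kd, cycles 3-12 | 70 | 52.5 | 53 | 42 |
| KRd/KPd, cycle 1 day 8 through cycle 2 | 27 | 20.25 | 20 | 42 |
| KRd/KPd, cycles 3-12 | 56 | 42 | 42 | 42 |

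Section 7.1.1.2.1 agrees with the 25% rule in every row, after rounding. The footnote fails in two rows.

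**Size for KRd and KPd, cycles 1-2.**

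- Doses affected: 4 + 6 = 10 of 42.
- Per dose: 42/20 = 2.10 times the intended dose; 42/27 = 1.56 times the unreduced dose.
- Per week on the twice-weekly schedule: 2 × 42 = 84 mg/m², against 2 × 20 = 40 intended and 2 × 27 = 54 unreduced.
- Cumulative, Section 7.1.1.2.1: 2 × 15 + 10 × 20 = 230 mg/m².
- Cumulative, footnote b: 2 × 15 + 10 × 42 = 450 mg/m².
- Cumulative, unreduced: 2 × 20 + 10 × 27 = 310 mg/m².
- Ratios: 450/230 = 1.96; 450/310 = 1.45.

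For reference, Section 5.4.2 reports weekly KPd totals of up to 70 mg/m² (first relapse) and 54 mg/m² (advanced disease) as tolerated on a twice-weekly schedule; 84 is above both.

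**Kd, cycles 3-12.** Taken alone, 42/70 = 0.60 is a 40% cut. The cycle 3 rule gives 70 × 0.75 = 52.5, in line with 53, so a site that applies it has essentially no gap.

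**Effect on the cumulative-dose endpoint.** The full unreduced triplet dose is 310 + 30 × 56 = 1990 mg/m². One fully dosed patient given the footnote figure shifts by (450 − 230)/1990 = 11.1 percentage points, or 11.1/25 = 0.44 points on a 25-subject arm mean. If the denominator were instead the hepatic-reduced plan, 230 + 30 × 42 = 1490, the shift is 220/1490 = 14.8 points, or 0.59 on the arm mean. The documents do not say how many patients have mild impairment. If 1 to 3 of 25 were both impaired and misdosed (an assumption), the arm mean moves by 0.4 to 1.3 points on the first denominator and 0.6 to 1.8 on the second.

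**The case against.** The governing instruction is correct and stated more than once. The footnote itself orders a 25% cut, and its mg/m² figures are only a parenthesis. Section 7.1.1.2 and the Schedule of Activities send sites to the right place ("see Section 7.1.1.2.1 for modification of the initial dose"; and "For cycle 3, for subjects who were previously dose reduced, see Section 7.1.1.2 for starting dose"). Table 7-2 is introduced for managing toxicity, not for setting starting doses, and its 27 row shows 20 as the first reduction. To go wrong, a site must accept a rise from 27 to 42 as a reduction. The pharmacy manual, which is outside these documents, may also give the right doses.

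Much of this stands, and it makes the error unlikely. It does not make the footnote right. The footnote presents 42 as the meaning of the 25% rule, not as an example. The cross-references speak of the initial or starting dose, whereas the error begins on day 8 and the footnote claims the later doses too. The 20 in the 27 row is a toxicity step rather than the hepatic rule: the 56 row steps to 45, not 42. The covariate list in Section 10.2.2 also points readers to Section 7.4.1.1.1 for chronic mild impairment, although that is not a dosing instruction.

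Three limits are accepted. The Kd mismatch is largely resolved by the cycle 3 rule, and any remaining misreading lowers the dose. The tolerated weekly doses in Section 5.4.2 are KPd data and are not stated ceilings. The choice of denominator for the endpoint shift is open, but the shift is small either way.

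**Conclusion.** The concern holds. Footnote b is wrong as written for KRd and KPd from cycle 1 day 8 through cycle 2: 42 instead of 20 mg/m² per dose, and 450 instead of 230 mg/m² over the two cycles. These sizes apply only if a site doses from the footnote and overlooks both its percentage and Section 7.1.1.2.1, so they describe a possible error, not an expected one. Only patients with mild impairment at baseline are exposed.

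The reason to act is patient safety, not the analysis. Amendment 4 was issued to correct carfilzomib dosing errors, among them a Kd dose entered for KRd in cycle 1 and a hepatic dose that was off by 1 mg/m². This one is of the same kind, with a gap of 22 mg/m². It should be fixed.

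Section 7.4.1.1.4 has a lesser fault of the same type. Its re-escalation rule is sound, since the limit is the dose planned for the cycle, but the bracket lists only the Kd doses of 56 and 70 mg/m². The triplet plan is 27 and 56.

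**What to change.** Replace the bracketed figures in Table 7-2 footnote b with a reference to Section 7.1.1.2.1, or list them by arm:

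- All arms: 15 mg/m² on cycle 1 days 1-2.
- Kd: 42 mg/m² from cycle 1 day 8 through cycle 2, then 53 mg/m² in cycles 3-12.
- KRd and KPd: 20 mg/m² from cycle 1 day 8 through cycle 2, then 42 mg/m² in cycles 3-12.

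In the same change, state the ceiling in Section 7.4.1.1.4 by arm: Kd 56 mg/m² twice weekly or 70 once weekly; KRd and KPd 27 twice weekly or 56 once weekly.

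The cost is a clarification letter or a short amendment. Every figure is already in Table 7-1 or Section 7.1.1.2.1, and neither data collection nor analysis changes.
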